- ^w Although visit windowing for dosing days allows for \pm 7 days around any expected visit day, the interval between study drug administrations from one biweekly visit to the following biweekly visit must be between 8 and 20 days.
- ^x There should be a telephone call to the participant the day after the first infusion.

APPENDIX 6
Study Flow Chart for Study Period B: IV Dosing

	W1 and Every 4 Weeks Thereafter ^a	W13	W25	W53	W77	W105	W157 and Every 52 Weeks Thereafter	ET/SFU Last Dose + 16 W ^b
Assessment window	(± 7d)	(± 7d)	(± 7d)	(± 7d)	(± 7d)	(± 7d)	(± 7d)	(± 7d)
Informed consent	x ^c							
Vital signs ^d	x	x	x	x	x	x	x	x
Weight	x	x	x	x	x	x	x	x
Urinalysis ^e				x		x	x	x
Urine pregnancy test ^f	x	x	x	x	x	x	x	x
PK serum sample ^g						x	x	x
Serum ADA sample ^g						x		x
PD plasma sample ^h				x		x	x	x
Single 12-Lead ECG ⁱ				x		x	x	x
Physical and neurologic examinations ^j				x		x	x	x
Serum chemistry and hematology ^{k, l}				x		x	x	x
MRI ^m						x		
Optional CSF ^{n, p}						x		
Optional Tau-PET ^{o, p}						x		
Amyloid-PET ^p						x		

Appendix 6
Study Flow Chart for Study Period B: IV Dosing (cont.)

	W1 and Every 4 Weeks Thereafter ^a	W13	W25	W53	W77	W105	W157 and Every 52 Weeks Thereafter	ET/SFU Last Dose + 16 W ^b
Assessment window	(± 7d)	(± 7d)	(± 7d)	(± 7d)	(± 7d)	(± 7d)	(± 7d)	(± 7d)
Evaluate criteria for MCI/AD			x	x	x	x	x	
GDS ^{q,r}			x	x	x	x	x	
SMC ^{q,r}			x	x	x	x	x	
API ADAD Cognitive Composite Battery ^s			x	x	x	x	x	
FCSRT ^s			x	x	x	x	x	
Trail Making Tests A and B ^s			x	x	x	x	x	
RBANS ^s			x	x	x	x	x	
SPCQ ^{r,t,u}			x	x	x	x	x	
CDR ^{q,r,t}			x	x	x	x	x	
FAST ^{r,t}			x	x	x	x	x	
NPI ^{r,t}			x	x	x	x	x	
Suicidality assessment ^{q,r}			x	x	x	x	x	
Study drug administration ^{v,w,x}	x	x	x	x	x	x	x	
Concomitant medication review ^r	x	x	x	x	x	x	x	x
Adverse event review ^r	x	x	x	x	x	x	x	x

AD = Alzheimer's disease; ADA = anti-drug antibody; ADAD = autosomal-dominant Alzheimer's disease; API = Alzheimer's Prevention Initiative; CDR = Clinical Dementia Rating; CERAD = Consortium to Establish a Registry for Alzheimer's Disease; CSF = cerebrospinal fluid; d = day; ET = early termination; FAST = Functional Assessment Staging of Alzheimer's Disease; FCSRT = Free and Cued Selective Reminding Test; GDS = Geriatric Depression Scale; MCI = mild cognitive impairment; MMSE = Mini-Mental State Examination; MRI = magnetic resonance imaging;

Appendix 6

Study Flow Chart for Study Period B: IV Dosing (cont.)

NPI = Neuropsychiatric Inventory; PD = pharmacodynamic; PET = positron emission tomography; PK = pharmacokinetic; RBANS = Repeatable Battery for the Assessment of Neuropsychological Status; SFU = safety follow-up; SMC = Subjective Memory Checklist; SPCQ = Study Partner Characterization Questionnaire; W = week.

- ^a Week 1 is the first dose in Study Period B and may occur on the same day as the final ET-A or ET-B visit in Study Period A after all ET assessments are completed and the investigator deems dosing is appropriate.
- ^b Early termination visit/SFU visit, occurring when someone terminates prior to the end of the Study Period B, should be done 16 weeks after the last dose of study drug. Participants who continue crenezumab treatment after the end of Study Period B will not have a “last dose + 16 weeks visit”.
- ^c Informed consent to continue into Study Period B must be obtained at or before the Week 1 visit in Study Period B.
- ^d Vital signs include measurements of pulse rate, systolic and diastolic blood pressure, respiratory rate, and body temperature. The same arm should be used for all blood pressure measurements. Participants should rest for ≥ 3 minutes in a quiet room before pulse rate and blood pressure are measured. On study drug administration days, vital sign assessments should be performed just prior to the infusion, at the end of IV infusion, and ≥ 60 minutes after the end of the IV infusion.
- ^e Urinalysis will be performed by dipstick for pH, protein, glucose, ketones, nitrites, bilirubin, blood, specific gravity, leukocyte esterase, urobilinogen. Microscopic examination should be performed at the central laboratory if blood and/or protein results are positive.
- ^f Females of childbearing potential (including those who have had a tubal ligation) must have a pregnancy test (urine is preferred, but can be replaced with blood if urine sample cannot be collected) prior to each dose administration. If a urine pregnancy test is positive, it must be confirmed by a serum pregnancy test at the central laboratory.
- ^g PK and ADA samples should be obtained prior to study drug administration on the same day of dosing. Accurate recording of the time of study drug administration and pharmacokinetics is critical. Unscheduled PK samples should be taken in the event of anaphylaxis, anaphylactoid, or serious or severe hypersensitivity reactions. For any participant suspected of developing anaphylaxis, or anaphylactoid or serious or severe hypersensitivity reactions warranting discontinuation of dosing, ADA and concurrent PK samples as well as any clinically relevant samples (such as total tryptase) should be collected as close as possible to the event, and then at 4 and 8 weeks postdose.
- ^h PD plasma sample collection prior to study drug administration.
- ⁱ Perform after the participant has been at rest in a supine position. Electrocardiograms for each participant should be obtained from the same machine whenever possible and performed prior to any other assessments (e.g., vital signs).
- ^j Complete physical and neurologic examinations should include an evaluation of the head, eyes, ears, nose, and throat, and the cardiovascular, dermatologic, musculoskeletal, respiratory, gastrointestinal, and neurologic systems. Neurologic examinations should include assessment of mental status, level of consciousness, cranial nerve function (including fundoscopic examination), motor function, sensory function, reflexes, coordination, and assessment of gait. Other examination components or systems may be assessed as clinically indicated. Symptom-directed physical and neurologic examinations may be done at any other visit as needed to assess the safety of the participant.
- ^k Serum chemistry includes sodium, potassium, BUN, bicarbonate, estimated glomerular filtration rate, calcium, AST, ALT, γ -glutamyl transpeptidase, total and direct bilirubin, alkaline phosphatase, lactate dehydrogenase, total protein, albumin, glucose, cholesterol, triglycerides, uric acid, creatine phosphokinase, and glycosylated hemoglobin.

Appendix 6
Study Flow Chart for Study Period B: IV Dosing (cont.)

- ^l Hematology includes WBC count with differential, RBC count, hemoglobin, hematocrit, and platelet count.
- ^m MRIs should be done at Week 105 or ET if ET is prior to Week 105. However, MRI may be done at any visit if clinically indicated for new or unexplained neurologic symptoms.
- ⁿ For the optional CSF sample, only those participants that previously consented to these optional assessments in Study GN28352 have the option to continue to provide samples in this study. A separate *consent signature* is required for each of this assessment. Cerebrospinal fluid samples should be collected prior to dosing on the same day of dosing or the day prior to dosing. It is critical that the actual date and the time of sample collection is recorded. A follow-up phone call should be made to the participant the day after the CSF collection. The CSF sample will also be used to determine crenezumab CSF concentration.
- ^o *Optional tau-PET scan, only for those participants who previously consented to these optional tau PET substudy.*
- ^p Cerebrospinal fluid and/or PET assessments to be performed at Week 105 or ET if ET is prior to Week 105. Cerebrospinal fluid and/or PET assessments will not be performed at the ET visit if less than 6 months have elapsed since the previous CSF and/or PET assessment. If needed because of operational constraints, CSF and/or PET assessments can be performed up to 3 months after Week 105. Cerebrospinal fluid and PET assessments should not be done on the same day, but at least 24 hours apart. Amyloid PET and Tau PET assessments should not be done on the same day, but at least 24 hours apart.
- ^q Cognitive and selected other assessments (GDS, SMC, CDR, and suicidality assessment) should not be administered to the participant immediately after dosing or any potentially stressful procedures (e.g., blood draws, CSF sampling, imaging). Also, participants should not perform these assessments while fasting. For each participant, best efforts should be exerted to perform subsequent assessments at the same time of day as the baseline assessments.
- ^r In exceptional instances, these assessments are permitted by phone or video technology.
- ^s The API ADAD Composite Cognitive Test Battery includes the following assessments which should be administered in this order: MMSE, Multilingual Naming Test, Word List: Memory, CERAD Constructional Praxis, Word List: Recall, Word List: Recognition, Raven's Progressive Matrices—Set A. The API ADAD composite should also be administered before administering FCSRT, Trail Making Test, and RBANS.
- ^t The SPCQ, CDR (study partner portion), FAST, SMC, and NPI should be administered to the same study partner throughout the study. Best efforts should be exerted in order for the study partner to be present for all visits requiring study partner assessments. In rare instances, for which the study partner cannot be present in person, these assessments may be administered by telephone.
- ^u Completed prior to the administration of all other study partner assessments at each visit.
- ^v Study drug administration should be performed only after all assessments/rating scales have been completed (unless indicated otherwise). Study drug will be administered to participants by injection (full details in the pharmacy manual). Participants must be observed for a minimum of 60 minutes after dosing.
- ^w Although visit windowing for dosing days allows for \pm 7 days around any expected visit day, the interval between study drug administrations from 1 monthly visit to the following monthly visit must be between 21 and 35 days.
- ^x There should be a telephone call to the participant the day after the first infusion.

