2.5 STUDY PERIOD B OBJECTIVES

The objectives of Study Period B are:

- *Provide continued drug access to study participants until the regulatory approval of crenezumab or another mechanism of post-trial access to crenezumab is initiated*
- *Assess the long-term safety, efficacy, and PK and PD effects of crenezumab*

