The study duration for individual participants will be at least approximately 284 weeks, including an 8-week screening period, a double-blind treatment period of at least 260 weeks in length, a 4-week final dose visit, and a final safety follow-up visit 16 weeks after the last dose of study drug (crenezumab or placebo) that will allow for clinical follow-up after treatment discontinuation for participants who do not continue with study drug beyond the end of Study Period A or who terminate study drug early. One or more interim analyses may be performed at the Sponsor's discretion (see Sections [3.2](#) and [4.10.9](#)).

Study Period B: Following the completion of Study Period A, participants will be offered the opportunity to continue to receive study drug until *regulatory approval or another mechanism for post-trial access to crenezumab* is started (via an OLE or other programs) or development of crenezumab is discontinued. This is termed Study Period B (see Sections [3.2.1](#), [4.5.5](#), [4.5.8](#)). All *PSEN1* mutation carriers will be provided crenezumab in Study Period B regardless of treatment allocation during Study Period A and all non-carriers will continue on placebo. Treatment allocation for both Study Periods A and B will remain blinded. Study Period B may last up to approximately 3–3.5 years depending on when participants enter Study Period B and when crenezumab is granted *regulatory approval or development of crenezumab* is discontinued. See [Figure 2](#).

See [Appendix 1](#) and [Appendix 2](#) for the study flowchart for SC dosing.

[figure not shown]
See [Appendix 3](#) and [Appendix 4](#) for the study flowchart for IV dosing.

Figure 1 Study Design

PSEN1 = presenilin 1; RCT = randomized, controlled trial.

Figure 2 Study Schematic

3.2

RATIONALE FOR STUDY DESIGN

Study Period A: The study will utilize a common-close design. All participants will be enrolled in the double-blind portion of the study until the last ongoing participant who is enrolled in the study and remains on treatment (i.e., ongoing enrolled participant) has received approximately 260 weeks of treatment, as far as is practical (see Section 4.5.4). All participants will not have the same amount of follow-up after enrollment but all will have at least 5 years of double-blind treatment.

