5.1.3 Protocol-Defined Events of Special Interest/Non-Serious Expedited Adverse Events

The following events are events of special interest and will need to be reported to the Sponsor expeditiously (i.e., no more than 24 hours after learning of the event; see Section 5.4 for reporting instructions), irrespective of regulatory seriousness criteria:

- ARIA-E (cerebral VE or sulcal effusion) (see Section 3.5.2)
- ARIA-H
 - Superficial siderosis of the CNS (see Section 3.5.2)
 - Cerebral microhemorrhages (see Section 3.5.2)
- Macrohemorrhages (see Section 3.5.2)
- Occurrence of pneumonia verified by imaging (e.g., chest X-ray) (see Section 3.5.3)
- The finding of an elevated ALT or AST $>3 \times$ ULN in combination with either an elevated total bilirubin ($>2 \times$ ULN) or clinical jaundice in the absence of cholestasis or other causes of hyperbilirubinemia is considered to be an indicator of severe liver injury. Therefore, investigators must report as an adverse event cases of potential drug-induced liver injury that include the occurrence of either of the following:
 - Treatment-emergent ALT or AST $>3 \times$ ULN in combination with total bilirubin $>2 \times$ ULN
 - Treatment-emergent ALT or AST $>3 \times$ ULN in combination with clinical jaundice
- Suspected transmission of an infectious agent by the investigational product, as defined below
 - Any organism, virus, or infectious particle (e.g., prion protein transmitting transmissible spongiform encephalopathy), pathogenic or non-pathogenic, is considered an infectious agent. A transmission of an infectious agent may be suspected from clinical symptoms or laboratory findings that indicate an infection in a participant exposed to a medicinal product. This term applies only when a contamination of the study drug is suspected.

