Single 12-Lead ECG ⁱ				x		x	x	x
Physical and neurologic examinations ^j				x		x		x
Serum chemistry and hematology ^{k,l}				x		x		x
MRI ^m						x		
Optional CSF ^{n,p}						x		
Optional Tau-PET ^{o,p}						x		
Amyloid-PET ^p						x		
Evaluate criteria for MCI/AD			x	x	x	x	x	
GDS ^{q,r}			x	x	x	x	x	

Appendix 5
Study Flow Chart for Study Period B: SC Dosing (cont.)

	W1 and Every 2 Weeks Thereafter ^a	W13	W25	W53	W77	W105	W157 and Every 52 Weeks Thereafter	ET/SFU Last Dose + 16 W ^b
Assessment window	(±7d)	(±7d)	(±7d)	(±7d)	(±7d)	(±7d)	(±7d)	(±7d)
SMC ^{q,r}			x	x	x	x	x	
API ADAD Cognitive Composite Battery ^s			x	x	x	x	x	
FCSRT ^s			x	x	x	x	x	
Trail Making Tests A and B ^s			x	x	x	x	x	
RBANS ^s			x	x	x	x	x	
SPCQ ^{u,r,t}			x	x	x	x	x	
CDR ^{q,r,t}			x	x	x	x	x	
FAST ^{r,t}			x	x	x	x	x	
NPI ^{r,t}			x	x	x	x	x	
Suicidality assessment ^{q,r}			x	x	x	x	x	
Study drug administration ^{v,w,x}	x	x	x	x	x	x	x	
Concomitant medication review ^r	x	x	x	x	x	x	x	x
Adverse event review ^r	x	x	x	x	x	x	x	x

AD = Alzheimer's disease; ADA = anti-drug antibody; ADAD = autosomal-dominant Alzheimer's disease; CDR = Clinical Dementia Rating; CERAD = Consortium to Establish a Registry for Alzheimer's Disease; CSF = cerebrospinal fluid; d = day; ET = early termination; FAST = Functional Assessment Staging of Alzheimer's Disease; FCSRT = Free and Cued Selective Reminding Test; GDS = Geriatric Depression Scale; MCI = mild cognitive impairment; MMSE = Mini-Mental State Examination; MRI = magnetic resonance imaging; NPI = Neuropsychiatric Inventory; PD = pharmacodynamic; PET = positron emission tomography; PK = pharmacokinetic; RBANS = Repeatable Battery for the Assessment of Neuropsychological Status; SFU = safety follow-up; SMC = Subjective Memory Checklist; SPCQ = Study Partner Characterization Questionnaire; W = week.

Appendix 5
Study Flow Chart for Study Period B: SC Dosing (cont.)

- ^a Week 1 is the first dose in Study Period B and may occur on the same day as the final ET-A or ET-B visit in Study Period A after all ET assessments are completed and the investigator deems dosing is appropriate.
- ^b Early termination visit/SFU visit, occurring when someone terminates prior to the end of the Study Period B, should be done 16 weeks after the last dose of study drug. Participants who continue crenezumab treatment after the end of Study Period B will not have a “last dose + 16 weeks visit”.

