- ^j Complete physical and neurologic examinations should include an evaluation of the head, eyes, ears, nose, and throat, and the cardiovascular, dermatologic, musculoskeletal, respiratory, gastrointestinal, and neurologic systems. Neurologic examinations should include assessment of mental status, level of consciousness, cranial nerve function (including fundoscopic examination), motor function, sensory function, reflexes, coordination, and assessment of gait. Other examination components or systems may be assessed as clinically indicated. Symptom-directed physical and neurologic examinations may be done at any other visit as needed to assess the safety of the participant.
- ^k Serum chemistry includes sodium, potassium, BUN, bicarbonate, estimated glomerular filtration rate, calcium, AST, ALT, γ -glutamyl transpeptidase, total and direct bilirubin, alkaline phosphatase, lactate dehydrogenase, total protein, albumin, glucose, cholesterol, triglycerides, uric acid, creatine phosphokinase, and glycosylated hemoglobin.
- ^l Hematology includes WBC count with differential, RBC count, hemoglobin, hematocrit, and platelet count
- ^m MRIs should be done at Week 105 or ET if ET is prior to Week 105. However, MRI may be done at any visit if clinically indicated for new or unexplained neurologic symptoms.

Appendix 5
Study Flow Chart for Study Period B: SC Dosing (cont.)

- ⁿ For the optional CSF sample, only those participants that previously consented to these optional assessments in Study GN28352 have the option to continue to provide sample in this study. A separate optional *consent signature* is required for this assessment. Cerebrospinal fluid samples should be collected prior to dosing on the same day of dosing or the day prior to dosing. It is critical that the actual date and the time of sample collection is recorded. A follow up phone call should be made to the participant the day after the CSF collection. The CSF sample will also be used to determine crenezumab CSF concentration.
- ^o *Optional tau-PET scan, only for those participants who previously consented to these optional tau PET substudy.*

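### In Study Period B, the SC flowchart schedules no on-treatment examination or safety bloods after Week 105; the IV flowchart does

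*Protocol*

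**What the plan says.** Appendix 5 (SC) and Appendix 6 (IV) of the protocol use the same eight visit columns for Study Period B: W1 and each dosing visit, W13, W25, W53, W77, W105, W157 (repeating every 52 weeks), and ET/SFU, which falls 16 weeks after the last dose.

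- In Appendix 5, the rows "Physical and neurologic examinations ^j" and "Serum chemistry and hematology ^{k,l" are marked at W53, W105 and ET/SFU.
- In Appendix 6, the examination row and the row "Serum chemistry and hematology ^{k, l" are marked at W53, W105, W157 and ET/SFU.
- Footnote b, in both charts, removes the last visit for some: "Participants who continue crenezumab treatment after the end of Study Period B will not have a" follow-up visit at last dose plus 16 weeks.
- Footnote j allows unscheduled checks: "Symptom-directed physical and neurologic examinations may be done at any other visit as needed to assess the safety of the participant".

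On duration, Section 3.1 states that "Study Period B may last up to approximately 3–3.5 years". Section 2.5 gives as a Period B objective: "Assess the long-term safety, efficacy, and PK and PD effects of crenezumab". Section 3.5.5 says that laboratory tests, including chemistry and hematology, and physical and neurological examinations run throughout the study. Section 4.5.8 allows Period B frequencies to differ from Period A and sends the reader to the two appendices. Neither section gives a reason for SC to differ from IV.

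**The concern.** Sites follow the flowchart, so a blank cell means the test is not scheduled. Under Section 5.1.3, "investigators must report as an adverse event cases of potential drug-induced liver injury", and that event is defined by ALT or AST above 3 times the upper limit of normal together with raised bilirubin or jaundice. It cannot be identified without liver chemistry. The remaining SC checks after W105 (adverse event review every 2 weeks, vital signs, ECG, urinalysis, symptom-directed examination, symptom-driven MRI) include no routine ALT/AST or blood count. The laboratory row is therefore the more important of the two.

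The examination row matters as well. Section 3.5.2.1 makes regular neurological examination part of ARIA monitoring, and Period B has only one scheduled MRI, at W105. Carriers who were on placebo in Period A first receive crenezumab in Period B, so the late visits belong to their first long exposure.

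**Working it through.** **Step 1. The two charts side by side.**

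| Row | SC (Appendix 5) | IV (Appendix 6) |
|---|---|---|
| Physical/neurologic examination | W53, W105, ET/SFU | W53, W105, W157, ET/SFU |
| Chemistry/hematology | W53, W105, ET/SFU | W53, W105, W157, ET/SFU |
| PD plasma sample | W77, W105, ET/SFU | W53, W105, W157, ET/SFU |
| ECG | W53, W105, W157, ET/SFU | W53, W105, W157, ET/SFU |
| Urinalysis | W53, W105, W157, ET/SFU | W53, W105, W157, ET/SFU |
| PK serum sample | W105, W157, ET/SFU | W105, W157, ET/SFU |

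**Step 2. Is the W157 difference systematic?** Each chart has 30 assessment rows. In the W157 column 27 agree, including ADA, MRI, CSF and both PET rows, which are blank in both charts. Three differ: examination, chemistry/hematology and the PD sample. A deliberately lighter SC visit would not be expected to keep ECG, urinalysis and a PK draw while dropping liver chemistry.

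**Step 3. Could the marks have shifted?** Both SC rows have all eight cells, and the last mark falls under ET/SFU. The ECG row directly above has its W157 mark. A shifted column is not the natural reading.

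**Step 4. Length of the gap.** Inputs: Period B of 3 to 3.5 years (Section 3.1), the visit weeks above, and 52 weeks per year.

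- End of Period B: 3 × 52 = W156; 3.5 × 52 = W182.
- SC, on treatment after W105, at 3.5 years: 182 − 105 = 77 weeks.
- IV, longest interval: 157 − 105 = 52 weeks.
- Excess at 3.5 years: 77 − 52 = 25 weeks, which is one missed examination and one missed draw.
- Excess at 3 years: 0, because W156 comes before W157.
- To the follow-up visit at 3.5 years: 182 + 16 = W198. SC: 198 − 105 = 93 weeks. IV: 52 weeks to W157, then 198 − 157 = 41 weeks.

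Using 52.18 weeks per year moves the 3.5-year figures by less than a week (77.6 and 93.6).

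**Step 5. Participants without the follow-up visit.** For an SC participant who continues crenezumab after Period B, footnote b removes ET/SFU. W105 is then the last scheduled examination and safety blood test in this protocol. The footnote also applies on IV, but there the W157 tests remain.

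**The case against.** The strongest reply is that the effect is small and the reading depends on where marks sit in a table.

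- **Layout.** Other flowcharts in this protocol have marks that look misplaced. In Appendix 3, physical examination falls at W80 while neurological examination and the other major assessments fall at W76. The SC PD row in Appendix 5 also looks odd. This is a fair reason to check the typeset page, but Step 3 makes lost marks the less likely explanation.
- **Size.** The excess is nil at 3 years and one visit at 3.5 years. Later entrants may never reach W157, participants may move to IV on entering Period B (Section 3.2.1), and some SC participants are non-carriers on placebo. All of this stands and limits the number affected.
- **Other checks.** The W157 urinalysis dipstick includes bilirubin and urobilinogen, and a suspicious adverse event can prompt unscheduled bloods. The protocol's summary of earlier trials describes no hepatic signal, and one annual draw is a weak detector of liver injury. These points soften the concern, but none supplies scheduled ALT/AST or blood counts.
- **Intent.** IV gives about 4-fold higher exposure, so lighter SC monitoring is conceivable. The documents do not say so, and Section 3.5.5 points the other way.
- **Follow-up figure.** The 93 weeks include 16 weeks off treatment, so the on-treatment figure of 77 weeks is the one to use.

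**Conclusion.** The concern holds. On the charts as published, SC participants in Period B have no scheduled on-treatment physical/neurologic examination, chemistry or hematology after W105, while IV participants have all of these at W157. Monitoring is reduced, not absent. The excess over IV ranges from 0 weeks (Period B of 3 years) to about 25 weeks (3.5 years), with one examination and one draw lost per affected participant. The number affected cannot be worked out from the documents. The conclusion assumes that the marks are in their intended columns and that no unstated reason exists for treating SC differently. The correction should be made because it closes a gap in long-term safety data at almost no cost.

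**What to change.** In Appendix 5, mark the W157 column (and so every 52 weeks after it) for physical/neurologic examination and for serum chemistry/hematology, to match Appendix 6. At the same time, check the SC PD row, which has W77 where IV has W53 and lacks W157, against the intended schedule. If the lighter SC schedule is deliberate, state the reason in Section 4.5.8 or in a footnote.

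The cost is a correction to two flowchart rows, plus one examination and extra tubes at a visit that already takes place and already includes a PK blood draw.
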